5.8 Dietary Restrictions

Subjects will fast overnight for at least 8 hours prior to the clinical safety labs at Screening.

Subjects should not take any food for at least 45 minutes or more prior to scheduled ORMD-0801 (or placebo) dosing as described in the study design. All subjects will be provided with a standardized diabetic breakfast on Day 1, then continuing from dinner on Day 2 through breakfast on Day 10. Standardized snacks will be provided between breakfast and lunch, between lunch and dinner, and between dinner and bedtime.

Excessive caffeine use (i.e., more than five cups of caffeinated beverages per day) will not be allowed from Screening through the Follow-Up Visit 3. Excessive alcohol use or binge drinking will be discouraged during the study, and alcohol will be prohibited 72 hours prior to admission to the CRU (Visit 2/Period 1, 2, and 3/Day 1) and throughout the domiciled period (i.e., through the morning assessments on Day 10).

Subjects will also be asked to refrain from any unusual or unaccustomed vigorous exercise during the course of the study.

6 STUDY PROCEDURES AND ASSESSMENTS

6.1 Informed Consent

According to the ICH guideline for GCP (E6) and all institutional local, state, and federal laws, the Investigator will obtain and document informed consent for each subject screened for this study. All subjects will be informed in writing of the nature of the protocol and Investigational Drug, its possible hazards, and their right to withdraw at any time, and will sign a form (ICF) indicating their consent to participate in the study prior to the initiation of study procedures. The subject's medical record should contain written documentation indicating that informed consent was obtained. The ICF must be reviewed and approved by the Investigator's designated IRB and by Oramed Ltd. designee prior to its use. Refer to Section 11.1.4 for further details regarding informed consent.

6.2 Medical History and Prior Medications

At Screening, a complete medical history and social history, including smoking, caffeine, alcohol, and drug use, will be collected by subject interview. Medications and supplements, recent blood donations, illnesses, and participation in other Investigational Drug trials or clinical trials will also be recorded.

6.3 Safety Assessments

6.3.1 Weight and Height

Weight will be measured at all visits. Height will be measured at Screening only with the subject wearing no shoes.

6.3.2 Vital Signs

Vital signs (including seated SBP/DBP, and heart rate) will be recorded at all visits as described in Table 1. Temperature will be recorded at Visit 2/Day 2 only. Vital signs will be measured after the subject has been sitting for at least 5 minutes in a quiet environment and prior to any blood draw that occurs at the same time point. During Treatment Periods 1, 2, and 3, vital signs will be measured on Day 1, at admission on Day 2, immediately prior to morning dosing on Days 3-9, and on the morning of Day 10 prior to discharge. The recorded seated SBP/DBP value will be the mean of two measurements taken 2 minutes apart and always using the non-dominant arm.

6.3.3 Physical Examination

A physical examination will be performed at Screening and at Follow-Up Visit 3, or in case of Early Withdrawal. The physical examination will include the following organ or body system assessments: skin; head, eyes, ears, nose, and throat; thyroid; lungs; cardiovascular; abdomen (liver, spleen); lymph nodes; and extremities, as well as an abbreviated neurological examination.

6.3.4 12-Lead ECG

A 12-lead ECG will be performed at Screening. The 12-lead ECG will be recorded after the subject has been resting at least 5 minutes in the supine position in a quiet environment. ECGs

will be read for QT and QTc (Federicia's) intervals and clinically significant abnormalities. At the Investigator's discretion, an additional ECG may be performed at the end of treatment; however, it will be recorded in source documents as an unscheduled assessment.

6.3.5 Clinical Laboratory Tests

Blood and urine for clinical safety laboratory assessments will be collected and processed using standard procedures. A local laboratory will perform all clinical laboratory tests.

In the event of abnormal clinical laboratory values, the Investigator will make a judgment whether or not the abnormality is clinically significant.

6.3.5.1 Clinical Safety Labs

The clinical safety labs will include the following hematology, serum chemistry, and urinalysis tests:

Hematology

- Hematocrit
- Hemoglobin
- Mean corpuscular hemoglobin
- Mean corpuscular hemoglobin concentration
- Mean corpuscular volume
- Platelet count
- Red blood cell distribution width
- Red blood cell count
- White blood cell count with differential

Serum Chemistry

- Sodium
- Potassium
- Chloride
- Bicarbonate
- Alanine aminotransferase (ALT)
- Aspartate aminotransferase (AST)
- Gamma-glutamyltransferase (GGT)
- Total bilirubin
- Alkaline phosphatase
- Albumin
- Total Protein
- Blood urea nitrogen (BUN)
- Creatinine
- Uric acid
- Glucose
- Calcium
- Phosphorus
- Total cholesterol
- Triglycerides

Urinalysis

- Appearance (color and character)
- Bilirubin
- Urobilinogen
- Protein
- Glucose
- Ketones
- Leukocyte esterase
- Urine blood
- Nitrite
- pH
- Specific gravity

6.3.5.2 Pregnancy Test

A serum pregnancy test will be performed for WCBP at Screening. A urine pregnancy test will be performed for WCBP at treatment Periods 1, 2, and 3 (Day 2).

FSH testing to confirm menopause should be done for women who have had more than 24 months since their last menstrual cycle, who are younger than 55 years old, and who are not surgically menopausal.

6.3.5.3 Additional Screening Bloodwork

In addition to the blood tests listed above, HbA_{1c}, C-peptide, and thyroid stimulating hormone (TSH) will be measured at Screening.

6.3.5.1 Drugs of Abuse and Breathalyzer

Drugs of abuse urine screens will be completed at Screening and at Visit 2/Day 2 (all three treatment Periods) according to the laboratory manual provided by the local laboratory and will include testing for amphetamines, barbiturates, cocaine metabolites, opiates, benzodiazepines and cannabinoids. A breathalyzer test will also be performed at Screening and at Visit 2/Day 2 (all three treatment Periods).

6.4 Efficacy Assessments

6.4.1 Continuous Glucose Monitors (CGM)

A continuous glucose monitor (CGM) will be used to monitor patient glucose levels (including post-prandial) during Visit 2, Periods 1, 2, and 3. Further information about the device can be found in the laboratory manual.

Subjects will have the CGM implanted on Day 1 of each treatment Period. On Day 3, the cannula will be changed and the CGM will be re-implanted to collect data until the morning of Day 10. Staff will be advised regarding appropriate procedures in the event of nocturnal hypoglycemia.

6.5 Pharmacokinetic/Pharmacodynamic Assessments

Blood samples for PK/PD analysis of absorbed insulin based on C-peptide correction of total insulin levels will be collected during Visit 2, Periods 1, 2, and 3, on Day 3 and Day 8. An indwelling venous catheter may be inserted for the collection of blood samples if deemed necessary. One 4.5 mL sample of total whole blood will be collected for each blood draw.

On Day 3, blood samples will be collected at the following nominal time points relative to the scheduled (per randomization scheme) dose of placebo: predose (45 to 5 mins prior to dosing) and every 30 minutes (\pm 5 minutes) postdose until 5 hours has elapsed. On Day 8, blood samples will be collected at the following nominal time points relative to the scheduled (per randomization scheme) dose of study treatment (active or placebo): predose (45 to 5 mins prior to dosing) and every 30 minutes (\pm 5 minutes) postdose until 5 hours has elapsed. The total volume collected from each subject for PK/PD samples will be approximately 99 mL per treatment Period, for a total of 297 mL during the entire study. Actual blood sampling times must be recorded in the source and eCRF.

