The potential advantage of oral insulin in the treatment of elevated fasting blood glucose as compared to subcutaneously-administered insulin lies in its delivery to the hepatic portal vein. Orally-administered insulin, once transported across the gut wall, is ferried to the hepatic portal vein, mimicking the natural route of endogenous pancreatic insulin and delivering the insulin directly to the intended site of action. In contrast, subcutaneously-administered insulin reaches the liver through the systemic circulation thereby requiring higher systemic levels of insulin in order to achieve the same effect. Thus, oral insulin administration is expected to avoid systemic hyperinsulinemia and provide a markedly reduced risk of hypoglycemia. The PK/PD profile of ORMD-0801 is well-suited to the control of both fasting blood glucose and subsequent pre-meal blood glucose levels due to the delayed onset of glucose lowering activity. Therefore, Oramed is pursuing the oral administration of ORMD-0801 at bed time and one or two other times during the day for the improvement of glycemic control in adult subjects with type 2 diabetes mellitus.

Oramed has completed five Phase 1 safety studies of various formulations of ORMD-0801 in healthy human volunteers. Four Phase 2 studies have been completed, two in patients with type 2 diabetes, and two in patients with type 1 diabetes. These Phase 2 studies investigated different formulations, the effect of meals at different times following ORMD-0801 administration, and the effect of ORMD-0801 on glucose as measured by continuous glucose monitoring over a ten day treatment period with three doses per day prior to meals. Notably, one Phase 2 study

assessed the safety and effectiveness on fasting blood glucose of repeat bed time administration of ORMD-0801 in patients with type 2 diabetes over a period of 6 weeks. A Phase 1/2 dose-response study was also conducted. These studies demonstrated that the drug product is well-tolerated and can effectively reduce plasma glucose and C-peptide levels. There were no significant safety observations and no serious adverse reactions were reported for the completed studies, although there were two self-reported events of hypoglycemia in the six-week, Phase 2 study.

Oramed intends to continue with clinical development of ORMD-0801 under a U.S. IND application.

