2.2 Secondary Objectives

- To compare pre-treatment (Day 3) to end of treatment (Day 8) mean daytime CGM glucose for single and multiple doses of ORMD-0801 vs placebo.
- To compare pre-treatment (Day 3) to end of treatment (Day 8) mean nighttime CGM glucose for single and multiple doses of ORMD-0801 vs placebo.
- To compare pre-treatment (Day 3) to post-treatment washout (Day 9) 24-hour CGM glucose for single and multiple doses of ORMD-0801 vs placebo.
- To compare post-prandial glucose measurements for single and multiple doses of ORMD-0801 vs placebo.
- To compare pre-treatment (Day 3) to end of treatment (Day 8) insulin pharmacokinetics (PK) for single and multiple doses of ORMD-0801 vs placebo.
- To compare pre-treatment (Day 3) to end of treatment (Day 8) C-peptide pharmacodynamics (PD) for single and multiple doses of ORMD-0801 vs placebo.
- To compare defined events of hypoglycemia for single and multiple doses of ORMD-0801 vs placebo.

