8.2 Pharmacokinetic/Pharmacodynamic Evaluation

The PK/PD analysis will be conducted using model-independent methods and will be based on plasma concentrations of insulin and C-peptide.

Individual plasma concentrations of insulin and C-peptide will be listed for each subject and sampling time and summarized descriptively using the arithmetic mean, SD, CV (%), median, minimum and maximum. Individual plasma concentration-time profiles of insulin and C-peptide will be plotted on both a linear and a semi-logarithmic scale. Mean values will also be presented graphically.

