2.8.2. Pharmacokinetic / Pharmacodynamic Evaluations

Since Insulin is present in the subjects regardless of treatment, standard PK derivations do not apply.

The PK/PD measurements are taken pre-treatment (Day 3) and at end of treatment (Day 8). On Day 3, all subjects received Placebo, so these measurements will be used as the within subject control.

Time matched changes between Day 8 and Day 3 will be derived for the PK and PD parameters for each subject.

The following time intervals will be summarized: 0 to 60 minutes, 60 to 120 minutes, 120 to 180 minutes, 180 to 240 minutes, 240 to 300 minutes, 120 to 300 minutes and 180 to 300 minutes. Please note that the 0 to 60 minute interval will not be summarized, since it is believed that the study drug takes 60 minutes to metabolize.

The following parameters will be derived for Insulin C-Peptide for each subject:

- Positive Area (Area above 0),
- Negative Area (Area below 0),
- Absolute Area (Positive Area + the absolute value of the Negative Area),
- Maximum Difference,
- Time of Maximum Difference,
- Positive Area / hr (for the 120 to 300 minutes and 180 to 300 minutes intervals only),
- Negative Area / hr (for the 120 to 300 minutes and 180 to 300 minutes intervals only), and
- Absolute Area / hr (for the 120 to 300 minutes and 180 to 300 minutes intervals only).

The Positive Areas, Negative Areas and Absolute Areas will be compared using a one-way analysis of variance (ANOVA) with Fisher's LSD being used for pairwise treatment group comparisons.

The maximum difference and time of maximum difference will be compared in a pairwise fashion using the Wilcoxon Rank Sum test.

The PK/PD analysis will be conducted using model-independent methods and will be based on plasma concentrations of insulin and C-peptide. Individual plasma concentrations of insulin and C-peptide will be listed for each subject and sampling time and summarized descriptively using the arithmetic mean, SD, CV (%), median, minimum and maximum. Individual plasma concentration-time profiles of insulin and C-peptide will be plotted on both a linear and a semi-logarithmic scale. Mean values will also be presented graphically.

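### The protocol names C-peptide-corrected absorbed insulin as the PK quantity, but no analysis section defines it, and the planned Day 8 minus Day 3 insulin change mixes absorption with any drug-induced fall in the subject's own secretion

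*Protocol*

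**What the plan says.** Protocol 6.5 gives the purpose of the Day 3 and Day 8 samples as the PK/PD analysis of "absorbed insulin based on C-peptide correction of total insulin levels". The related secondary objective in Protocol 2.2 is "To compare pre-treatment (Day 3) to end of treatment (Day 8) insulin pharmacokinetics (PK) for single and multiple doses of ORMD-0801 vs placebo".

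The analysis sections do not carry the correction forward. Protocol 8.2 says the analysis "will be based on plasma concentrations of insulin and C-peptide", and SAP 2.8.2 repeats this. The SAP recognises the problem of the subject's own insulin: "Since Insulin is present in the subjects regardless of treatment, standard PK derivations do not apply". Its answer is the placebo day: "On Day 3, all subjects received Placebo, so these measurements will be used as the within subject control". It continues: "Time matched changes between Day 8 and Day 3 will be derived for the PK and PD parameters for each subject". Positive, negative and absolute areas of those changes are compared by one-way ANOVA with Fisher's LSD.

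In SAP 3.1 and 4.1, insulin and C-peptide have separate listings (16.2.6.6.1 to 16.2.6.7.2) and separate tables (14.2.5.1 and 14.2.5.2 against 14.2.6.1 and 14.2.6.2). The one joint output is Figure 14.2.4 in SAP 4.2, a by-subject plot with no derived parameter or test.

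**The concern.** The Day 3 subtraction handles secretion that is the same on both days. Comparison with the placebo period handles changes between the days that are unrelated to the drug. Neither handles a fall in the subject's own secretion that occurs only because active drug was given. The protocol's introduction reports that earlier studies showed the drug "can effectively reduce plasma glucose and C-peptide levels". C-peptide is the plan's own marker of endogenous insulin, so such a fall is to be expected on active Day 8.

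Other parts of the protocol make this matter more. The introduction describes delivery through the portal vein and an expectation that high systemic insulin is avoided, so the absorbed part seen in peripheral blood may be small. Exclusion criterion 8a removes subjects with C-peptide below 1.0 ng/mL, so everyone enrolled has appreciable secretion of their own.

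At stake is what the insulin PK comparison can conclude. A small or negative insulin change could mean little absorption, or absorption offset by suppression, and the planned insulin parameters cannot tell these apart.

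**Working it through.** **1. Are the samples for a correction available?** Predose plus 300/30 = 10 half-hourly draws gives 11 samples per sampling day. Then 11 × 2 days × 4.5 mL = 99 mL per period, and 99 × 3 = 297 mL, which reproduces both volumes in Protocol 6.5. Protocol 5.2 fixes one time of day for sampling in each period. Each Day 8 sample therefore has a Day 3 counterpart in the same period, at the same time after the same scheduled dose, with both analytes planned.

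**2. What the SAP variable measures.** Let I be total insulin, C be C-peptide, E3 be own insulin on Day 3, X be absorbed insulin on Day 8 and s be the fractional fall in own secretion caused by the drug.

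- Day 3 (placebo): I3 = E3
- Day 8 (active): I8 = (1 − s) × E3 + X
- SAP change: I8 − I3 = X − s × E3

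The change falls short of X whenever s > 0, and it reaches zero at s = X/E3.

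**3. What a proportional correction measures.** If own insulin moves in proportion to C-peptide at a given time point, then C8/C3 = 1 − s, and

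I8 − I3 × (C8/C3) = (1 − s) × E3 + X − (1 − s) × E3 = X.

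**4. Illustration at one time point.** The documents give no insulin or C-peptide values, so all inputs here are assumed, with E3 = 100.

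| X | s = 0 | 5% | 10% | 20% | 30% | Corrected |
|---|---|---|---|---|---|---|
| 5 | 5 | 0 | −5 | −15 | −25 | 5 |
| 10 | 10 | 5 | 0 | −10 | −20 | 10 |
| 20 | 20 | 15 | 10 | 0 | −10 | 20 |

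**5. Illustration for the planned areas.** The assumed profiles, with t in minutes, are own insulin 40 + 100·exp(−((t − 105)/60)²) and absorbed insulin 15·exp(−((t − 180)/50)²). Areas are trapezoidal on half-hourly values over 120 to 300 minutes, in unit-hours. The net area is not a SAP parameter; it is the sum of the positive and negative areas.

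| s | Positive | Negative | Net | Absolute | Corrected |
|---|---|---|---|---|---|
| 0 | 20.9 | 0.0 | 20.9 | 20.9 | 20.9 |
| 10% | 7.8 | −5.4 | 2.4 | 13.2 | 20.9 |
| 20% | 2.2 | −18.3 | −16.1 | 20.4 | 20.9 |
| 30% | 0.0 | −34.6 | −34.6 | 34.6 | 20.9 |

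The positive and net areas fall steadily as suppression grows. The absolute area does not: at 20% suppression it is almost what it is with none (20.4 against 20.9), although nearly all of it is then negative area.

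**The case against.** **The SAP follows the protocol's own statistical section.** This stands. Protocol 8.2 contains no correction either, and the only mention is in the sampling section. A reader might infer a plain protocol-versus-SAP departure, but the inconsistency already lies inside the protocol, between 6.5 and 8.2.

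**Suppression is not hidden.** C-peptide has its own objective, parameters and tables, and Figure 14.2.4 shows both analytes by subject. This stands in part. A fall in secretion would be visible beside insulin, but the formal insulin comparison would still be made on the mixed quantity.

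**The absence of a correction is inferred.** The table shells are in a separate file. In SAP 2.8.2, the sentence introducing the parameters runs the two analyte names together and could be read as a combined quantity. The separate listing and table titles argue against that reading. If a combined variable was meant, its formula is still missing.

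**Correcting by regression would be poorly founded.** This stands for a per-subject regression pooled over the 33 Day 3 pairs (11 × 3). Those pairs are serial draws from morning, afternoon and evening profiles under different meal conditions, and a fitted model sits badly with the plan's commitment to model-independent methods. A same-period ratio avoids the pooling, though it makes a proportionality assumption of its own.

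**The objective asks only for a comparison of insulin PK.** This stands: Protocol 2.2 does not ask whether oral insulin reaches the circulation. Protocol 6.5 nevertheless names absorbed insulin as the quantity the samples are for, and the plan should either define it or withdraw it.

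**Conclusion.** The point holds. The protocol names a PK quantity that no available analysis text or output title defines. The planned insulin change equals absorbed insulin minus the drug-induced fall in own secretion, so its positive and net areas understate absorption, and its absolute area mixes the two effects. The direction rests on s > 0, which the introduction supports from earlier studies.

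The size is unknown. The illustrations show how masking works and should not be read as forecasts for this trial. A reader might also infer that every planned insulin parameter is pulled towards no absorption. The absolute area contradicts that, since in the illustration it falls and then rises past its starting value. Nor can corrected insulin be equated with everything absorbed. Given the portal route the protocol describes, it reflects only what reaches peripheral blood.

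This concerns a secondary objective in a study stated not to be powered, so it bears on how the PK results may be interpreted and leaves the primary CGM comparison untouched.

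**What to change.** In SAP 2.8.2, define a C-peptide-corrected insulin variable from the same-period, time-matched Day 3 profile, for example I8 − I3 × (C8/C3) at each time point. Apply the planned intervals, areas and comparisons to it, present uncorrected insulin beside it, and add the matching listing and table. State what happens when any of the four values is missing. As a check, the variable should centre near zero in the placebo period, where X = 0. That tests the stability of the ratio without the drug, but not on it.

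The cost is SAP text, one derived variable and its outputs, with no new samples. The downside is the assumption that the insulin/C-peptide ratio at a given time point is stable from Day 3 to Day 8. Limiting the interpretation to insulin reaching peripheral blood should be stated with the results.

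If the sponsor does not want a correction, reconcile Protocol 6.5 with Protocol 8.2 and SAP 2.8.2, and state that the uncorrected insulin change will not be interpreted as absorbed insulin. Either choice should be settled before unblinding.

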6.6 Review and Documentation of Medications and Supplements

All medications or supplements subjects are taking or have taken within 30 days prior to Visit 2/Day 1 through Follow-Up Visit 3 will be recorded in the subject's medical record and the CRF.

All medications and supplements (other than study treatment) taken by the subject after Visit 2/Day 1 through Follow-Up Visit 3 assessments will be considered "concomitant" medications and supplements. Medications and supplements taken prior to Visit 2/Day 1 that are no longer being taken at Visit 2/Day 1 will be considered "prior" medications and supplements.

Medications and supplements should be recorded according to the generic name when possible. The use of concomitant medications and supplements should be limited to those that are medically necessary. Any medication or supplement used should have an indication recorded, and for concomitant medications and supplements, this indication must be represented as either for the treatment of an AE, for the management of a pre-existing condition, or for prophylaxis.

Dosage increases for any concomitant medication or supplement should be noted and the reason for the dosage increase recorded as an AE (assumes worsening condition). The side effects of concomitant medications will be recorded as AEs.

Any subject whose condition becomes disqualifying during the course of the study may be treated for that condition. If the condition is suspected during Screening, the subject should not be enrolled. Treatment of the condition should be instituted according to the Investigator's/attending physician's judgment.

Medications that have no treatment intent but rather are part of supportive routine care such as local anesthetics, intravenous solutions to maintain fluid balance and keep access open, medications used for prophylaxis, and narcotics for postsurgical pain must also be recorded in the subject's medical record and CRF.

